5.0 TREATMENT PLAN

5.1 Schema

5.2 Treatment Dosage and Administration

REGIMEN DESCRIPTION					
Agent	Premedications; Precautions	Dose	Route	Schedule	Cycle Length
Isatuximab	Montelukast 10 mg orally (C1 only) Dexamethasone 20 mg orally Acetaminophen/paracetamol 650 to 1000 mg orally. Diphenhydramine 50 mg orally (or equivalent: e.g., cetirizine, promethazine, dexchlorpheniramine, according to the approval availability) or diphenhydramine 25 50 mg IV (or equivalent). Intravenous route is preferred for at least the first four IV infusions.	10 mg/kg	IV	days 1,8,15 and 22 of cycle 1, then days 1 and 15 of cycles 2+	4 weeks (28 days)
Pomalidomide		3 mg	PO	days 1-21 of each cycle	
Dexamethasone		20 mg	PO	days 1, 8, 15, and 22 of each cycle	

5.3 Criteria for Initiating a New Cycle of Treatment

Subject must meet the following criteria to start a cycle of treatment:

- $ANC \geq 1.0 \times 10^9/L$.*
- Platelets $\geq 50 \times 10^9/L$ if $< 50\%$ of BM nucleated cells are plasma cells.*
- Platelets $\geq 30 \times 10^9/L$ if $\geq 50\%$ of BM nucleated cells are plasma cells (cycles 1-3 only)*
- All other treatment-related, non-hematologic toxicity (except for alopecia) must have resolved to \leq Grade 1 or to the subject's baseline condition. Treatment-emergent AEs that remain above Grade 1 but are NOT felt to be related to study treatment do not require delay in study therapy, but clinician should use his/her judgment in nonetheless delaying therapy if it is in the subject's best interest clinically.

*Supportive care interventions (growth factors, transfusions, etc.) as outlined in eligibility criteria may also be employed to achieve required cell counts prior to starting a cycle of therapy.

If the subject fails to meet the above start criteria for initiation of a next cycle of treatment, dosing should be delayed for 1 week. The subject should then be re-evaluated. If the subject continues to fail to meet the above-cited criteria, delay therapy again and continue to re-evaluate weekly. For delays of >2 weeks due to cytopenias felt to be due to therapy, see Table 3 in Section 5.4.2 below.

The maximum delay before study treatment should be permanently discontinued will be 6 weeks, unless a longer delay is clinically appropriate and approved by the study PI.

See section 5.4 for dose modifications and further guidance related to dose delays.

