8.0 EVALUATIONS AND ASSESSMENTS

8.1 Time and Events Table

Assessment	Screening ^{1c}	C1 D1 ²	C1 D8 ²	C1 D15 ₂	C1 D22 ²	C2 D1 ²	C2 D15 ²	C3 D1 ²	C3 D15 ²	C4+ D1 ²	C4+ D15 ²	EOT ³	Post- Treatment Visits ³ (Study)	Long- term Follow- up ³
Informed Consent	X													
Eligibility Verification	X													
Medical history	X ^{1a}	X				X		X		X		X	X	X
Physical exam	X ^{1a}	X				X		X		X		X	X	
Vital signs	X ^{1a}	X	X	X	X	X	X	X		X		X	X	
Karnofsky Performance Status	X	X				X		X		X		X	X	
Serum Pregnancy Test and Contraception Screening ^{1d, 1e}	X	X	X	X	X	X	X ^{1d}	X	X ^{1d}	X	X ^{1d}	X ^{1d}		
Skeletal Survey or WBLD-CT	X ^{1a}	As clinically indicated										X		
Plasmacytoma evaluation ¹⁰	X ^{1a}	As clinically indicated										X		
Bone marrow aspiration/biopsy ⁷	X ^{1b}	As clinically indicated										X		
Hematology ⁴	X ^{1c}	X	X	X	X	X	X	X				X	X	
Type and screen, red blood cell phenotyping (prior to isatuximab)		X												
Serum Chemistry ⁵	X ^{1c}	X	X	X	X	X	X	X		X		X	X	

Assessment	Screening ^{1c}	C1 D1 ²	C1 D8 ²	C1 D15 ₂ ²	C1 D22 ²	C2 D1 ²	C2 D15 ²	C3 D1 ²	C3 D15 ²	C4+ D1 ²	C4+ D15 ²	EOT ³	Post- Treatment Visits ³ (Study)	Long- term Follow- up ³
β-2-microglobulin and LDH	X	X										X		
M-protein quantification ⁶ and serum free light chain assay	X	X				X		X		X		X	X	
Blood biomarker collection ⁸		X ⁸								X ⁸		X ⁸	X ⁸	
Isatuximab IV		X	X	X	X	X	X	X	X	X	X			
Pomalidomide PO ¹²		X ¹²												
Dexamethasone PO ⁹		X	X	X	X	X ⁹								
Subject Pill Diary ¹⁴		X				X		X		X				
Clinical toxicity assessment (CTCAE v5.0) ¹¹	X	X	X	X	X	X	X	X	X ¹¹	X ¹¹	X ¹¹	X	X	
Concomitant medications review	X	X	X	X	X	X		X		X		X		
CARG-Global Assessment	X ⁸									X ⁸		X ⁸	X ⁸	
Gait speed test, PROMIS-cog, Mini-cog, ¹³	X ¹³									X ¹³		X ¹³	X ¹³	
IMWG Frailty assessment	X ⁸													
EORTC QLQ-C30, EORTC QLQ-MY20 QOL assessments ⁸		X ⁸								X ⁸		X ⁸	X ⁸	
Survival														X

Footnotes to Time and Events Table

1. Screening Windows for assessments are as follows:

- a. Complete history, physical exam and all imaging assessments should be performed within 21 days prior to day 1 of study treatment in cycle 1 except x-ray skeletal survey or WBLD-CT scan, which may be performed up to 4 weeks prior to cycle 1 day 1.
 - b. Baseline bone marrow biopsy/aspirate should be obtained within 4 weeks prior starting treatment on cycle 1 day 1.

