Post-treatment visits will be conducted for subjects who have an ongoing \geq grade 3 or serious AE (SAE) at the end of treatment visit and will be continued until the event is resolved or deemed irreversible by the investigator. These visits will occur at least once every 4 weeks (± 1 week) for the first 6 visits and then once every 12 weeks (± 2 weeks) thereafter. However, follow-up every 12 weeks by telephone or any other modality is permissible if a less frequent monitoring schedule is clinically appropriate, and if the subject would otherwise require removal from the study.

In addition, post-treatment visits will be conducted for subjects who remain progression free at their end of treatment visit and will occur once every 4 weeks (± 1 week) for the first 6 visits and then once every 12 weeks (± 2 weeks) thereafter until disease progression or the start of a new MM treatment. If follow up of \geq grade 3 or serious adverse events (as outlined above) has also concluded, patients will then enter the long-term follow-up phase. If possible, during the post-treatment phase, subjects should complete the Karnofsky performance status, CARG global assessment, quality of life assessment, cognitive testing, and blood correlatives every six months until they enter the long-term follow up phase.

The Long-Term Follow-up period will begin (except in the case of withdrawal of consent) after the end of treatment and post-treatment (if applicable as outlined above) visits and will take place every 3 months

(±2 weeks) for a maximum of 3-years from the end-of-treatment visit. Long-Term Follow-up visits will be limited to history of any subsequent cancer treatments, diagnosis of another cancer and survival status. Long-term follow up assessments may be conducted either in person, by telephone, via audio/video, medical record abstraction, or by other modality deemed appropriate for this purpose by the investigator.

After documented progression of MM and/or initiation of other, non-study therapy, follow-up should be every three months by any modality (telephone, via audio/video, or by other modality deemed appropriate for this purpose by the investigator).

4. Hematology: CBC with white blood cell differential

5. Serum chemistries must include the following:

- Every chemistry assessment: sodium, potassium, chloride, CO₂, BUN, creatinine, glucose, and calcium.

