8.4 Assessment of Efficacy

Any subject who receives treatment on this protocol will be evaluable for efficacy. Subjects who are withdrawn from the protocol before receiving any study treatment will not be evaluated for efficacy and will be replaced.

To assess disease status, MM labs will be performed as a baseline prior to treatment and then as outlined in the Time and Events Table.

This study will use the Consensus Criteria for Response by the International Myeloma Working Group (IMWG) Appendix O. Response Criteria for Multiple Myeloma [51].

The primary endpoint of the study is overall response rate as defined as the percentage of subjects achieving a partial response or better (\geq PR) to study therapy at any time (per IMWG criteria provided in Appendix O. Response Criteria for Multiple Myeloma).

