10.2 Sample Size and Accrual

Simon's two-stage design will be used with a total of 49 patients to test the response rate to isatuximab, low-dose pomalidomide, and dexamethasone among very elderly and/or otherwise highly toxicity-vulnerable patients. The null hypothesis that the response rate is 31% will be tested against a one-sided alternative. In the first stage, 25 patients will be accrued. If there are 7 or fewer responses in these 25 patients, the study will be stopped. Otherwise, 24 additional patients will be accrued for a total of 49. The null hypothesis will be rejected if 21 or more patients respond to the combination. This test has the type I error rate of 0.052 and power of 0.80 when the true response rate is 48%.

The predicted ORR is based on a subgroup analysis of elderly patients included in the randomized phase 3 ICARIA-MM trial, which demonstrated an ORR of 53.1% among patients on the Isa-Pom-Dex arm who were ≥ 75 years of age.[28] The ORR of patients ≥ 75 years treated on the control (Pd) arm was 31%. The population included in the current study is likely to be frailer overall than the ≥ 75 -year-old cohort included in ICARIA-MM. Furthermore, the response rates to may be somewhat lower given the starting pomalidomide dose of 3 mg.

Of note, the ORR among all patients treated with Isa-Pom-Dex on the ICARIA-MM trial was 60%, however the patients included in the current study will again be significantly older and more toxicity-vulnerable than the overall population of ICARIA-MM, which is expected to correlate with a lower ORR.

Based on accrual data from prior trials in refractory multiple myeloma at our institution, we estimate an accrual rate of approximately 2 eligible patients per month across all sites. We estimate that the enrollment period will be approximately 25 months and that the average duration on study will be approximately 10 months.

Sequential boundaries will be used to monitor unacceptable toxicity rate. Unacceptable toxicity is defined as a Grade 4 or higher non-hematological adverse

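### On-treatment disease assessment follows cycle Day 1 with no calendar rule during a hold, so progression may be dated late and PFS modestly overstated in subjects with more toxicity delays

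*Combined protocol and SAP*

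**What the plan says.** Section 8.4 leaves the timing of disease assessment to the schedule: "MM labs will be performed as a baseline prior to treatment and then as outlined in the Time and Events Table". In the 8.1 table, the row for M-protein quantification "and serum free light chain assay" is marked on treatment only at Day 1 of cycles 1, 2, 3 and 4+. The cycle is 28 days (5.2), and footnote 2 allows ±3 days around a visit.

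Section 5.3 delays a cycle by a week when start criteria fail, and then: "If the subject continues to fail to meet the above-cited criteria, delay therapy again and continue to re-evaluate weekly". The criteria are neutrophils, platelets and treatment-related non-hematologic toxicity; disease status is not among them. The maximum delay is 6 weeks unless the study PI approves a longer one, and no upper bound is given for that exception.

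Some disease assessment does not depend on Day 1. Footnote 7 sets marrow every 12 weeks in non-secretory disease, and imaging and other marrow samples are done as clinically indicated. After treatment, "post-treatment visits will be conducted for subjects who remain progression free at their end of treatment visit and will occur once every 4 weeks", but footnote 3 keeps that interval for 6 visits only and then moves to 12-weekly visits.

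PFS runs from first treatment to confirmed progression or death (3.2.9). Duration of response runs from PR to progression (3.2.8), with response dated at the initial test (Appendix O). Section 10.3.1 plans Kaplan-Meier estimates without formal comparisons and gives no rule for late or missed assessments.

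**The concern.** Progression is dated at the assessment that finds it. If Day 1 moves and the M-protein/FLC sample moves with it, the interval between assessments lengthens in exactly the subjects who are tolerating treatment worst. Poorer tolerability then lengthens observed PFS. That is an awkward dependence in a trial that selects toxicity-vulnerable subjects and treats tolerability as a main question.

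Delays are foreseeable. Section 1.7.1 reports grade 3/4 neutropenia in 85%, and pomalidomide dose reductions in 43%, of the Isa-Pom-Dex arm of the phase 3 trial it cites. Against that, this trial starts pomalidomide at 3 mg and lets supportive care be used to meet the count criteria.

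**Working it through.** **1. The plan's own figure.** The documents state no sample size or precision target for PFS or duration of response. The figure that can be reproduced is the ORR design in 10.2: a one-sided test of a 31% null rate, a first stage of 25 with futility at 7 or fewer responders, and a second stage of 24, making 49. The final rule reads: "The null hypothesis will be rejected if 21 or more patients respond to the combination". The probability of rejecting is the sum over x = 8 to 25 of P(X = x) × P(Y ≥ 21 − x), with X ~ Bin(25, p) and Y ~ Bin(24, p). This gives 0.0522 at p = 0.31 and 0.8001 at p = 0.48, agreeing with the stated 0.052 and 0.80. The rule uses only the count of responders at any time. No assessment interval enters it.

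**2. Longest gap within the 6-week limit.**
- No delay: 28 days.
- Sample only at the actual Day 1: 28 + 42 = 70 days, at most 42 days of extra lag.
- Sample at the planned Day 1 as well: intervals of 28 and 42 days, at most 14 days of extra lag.

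**3. Mean lag from true progression to detection.** With L the interval between assessments, mean lag = E[L²] / (2E[L]). Without delays, 28² / (2 × 28) = 14 days. The share and length of delays below are assumptions, and sampling is taken to occur only at the actual Day 1.

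| Cycles delayed | Delay | Mean lag (days) |
|---|---|---|
| 10% | 2 weeks | 882 / 58.8 = 15.0 |
| 20% | 2 weeks | 980 / 61.6 = 15.9 |
| 30% | 2 weeks | 1078 / 64.4 = 16.7 |
| 20% | 1–6 weeks, uniform | 1207.0 / 65.8 = 18.3 |
| 50% | 1–6 weeks, uniform | 1841.6 / 80.5 = 22.9 |
| 20% | 6 weeks | 1607.2 / 72.8 = 22.1 |
| 30% | 6 weeks | 2018.8 / 81.2 = 24.9 |

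The ceiling, every cycle 6 weeks late, is 35 days. If half the subjects have 30% of cycles delayed by 6 weeks, simulation gives them a mean lag of 3.6 weeks against 2.0 weeks in the rest.

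**4. If labs are also drawn at the planned Day 1.** A 2-week delay gives intervals of 28 and 14 days: (784 + 196) / (2 × 42) = 11.7 days, below 14. A 6-week delay gives 28 and 42 days: (784 + 1764) / (2 × 70) = 18.2 days, against 35 for a single 70-day gap.

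**5. Median PFS.** Progression times were simulated as exponential with a true median of 11.4 months, taken from the ≥75 subgroup in 1.7 as an illustration, and detected at the actual Day 1.
- No delays: 11.96 months.
- 2-week delays in 10–30% of cycles: 11.96.
- 6-week delays in 20% of cycles: 11.96.
- 6-week delays in 30% of cycles: 12.42.
- Uniform 1–6 week delays in 20–50% of cycles: up to 12.19.

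The shift due to delays is therefore 0 to 12.42 − 11.96 = 0.46 month. These medians move in steps because all dates fall on a weekly grid (11.96 months is week 52, 12.42 is week 54), so the mean lag is the steadier measure.

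**6. Duration of response.** Both ends are found at assessments. With 6-week delays in 30% of cycles and an assumed median time to response of 4 to 8 weeks after a 1-week offset, the mean bias is about −0.1 week if delays are spread evenly. It is −1.1 to −1.4 weeks if they fall only in the first three intervals, and +0.9 to +1.2 weeks if they fall only later.

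**The case against.** The strongest reply is that the effect is small and rests on assumed inputs. No delay rate is given. Supportive care may be used to reach the start criteria, and cytopenia delays beyond 2 weeks lead to consideration of G-CSF or a dose reduction (Table 4). The simulation counts progression only, whereas PFS also includes deaths, which are dated exactly. If all 49 subjects had exponential PFS events with median 11.4 months, the 95% interval would be 11.4 × exp(±1.96/√49), or 8.6 to 15.1 months, far wider than a 0.5-month shift. PFS is secondary and descriptive. All of this stands, and it limits the size of the point.

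It is also fair that failure of the start criteria is found at the planned Day 1, where a site may well draw the myeloma labs too. Nothing forbids it, but nothing requires it, and a 6-week hold would still leave 42 days to the next scheduled sample.

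Three stronger readings are tempting and are not supported:
- A reader might infer that duration of response is overstated. Its start is also detected late, so the bias has no fixed sign.
- A reader might infer that held subjects are always assessed less often than those off treatment. That is true only for the first 6 post-treatment visits; the later 12-weekly interval of 84 days exceeds 70.
- A reader might infer that comparison with historical trials is biased in a known direction. The documents do not say how those trials timed assessments.

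**Conclusion.** The gap is in the text: on-treatment M-protein/FLC testing follows cycle Day 1, Day 1 can slip by 6 weeks or more while only start criteria are re-checked, and neither the schedule nor the Kaplan-Meier plan corrects for it. Progression may therefore be dated later, and PFS modestly overstated, in subjects with more toxicity delays. Under the assumed partial-delay rates, mean lag is about 15–25 days instead of 14 and median PFS shifts by 0 to about 0.5 month, provided samples are taken only at the actual Day 1. The effect is smaller if sites also sample at the planned Day 1. The ORR decision rule, its type I error and its power are unaffected. This is worth correcting because the fix is cheap and removes a dependence of assessment timing on toxicity, not because it threatens the trial's main conclusion.

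**What to change.** State in 8.1 and 8.4 that on-treatment SPEP, UPEP, IFE and FLC are done every 4 weeks (±1 week) counted from C1D1, whether or not a cycle is delayed. For a delayed cycle this means a sample at the planned Day 1 and then at one of the weekly re-evaluation visits that 5.3 already requires. The interval matches the one footnote 3 uses for the first 6 post-treatment visits.

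The nominal gap becomes 28 days. It reaches 28 + 7 + 7 = 42 only if one sample is a week early and the next a week late, and it no longer depends on dosing. After a delay has shifted the cycles, no added visit is needed: from cycle 2, isatuximab visits on Days 1 and 15 are 14 days apart, so one always lies within a week of the due date.

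The cost is one sentence in each section and one or two extra samples per subject with a long delay (42 / 28 = 1.5). Because footnote 6 includes a 24-hour urine, each brings a urine collection as well as a blood draw. Dosing and delay rules do not change.

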5.4 Toxicities and Dosing Delays/Dose Modifications

Mid-cycle missed doses should not be made up. Missed doses should be skipped.

5.4.1 Isatuximab Dose Modifications/Delays

Dose modifications are not allowed with the exception of recalculating dose to account for weight changes of > 10% from cycle 1 day 1 weight.

For information on management of infusion reactions see Managing Infusion Reactions.

5.4.2 Pomalidomide Dose Modifications/Delays

Allowable dose adjustments/reductions are outlined in Table 3. If 1 mg is not tolerated despite maximal supportive care, then pomalidomide should be permanently discontinued and other study drugs may be continued if felt to be appropriate by the treating clinician.

Table 3 Pomalidomide Dose Levels/Modifications

Dose Level	Dose (mg)
+1*	4 mg
0	3 mg
-1	2 mg
-2	1 mg
-3	Discontinue

**If after 3-cycles, the patient has SD (<MR) and has not experienced any grade ≥ 3 hematologic toxicities or treatment-related grade ≥ 2 non-hematologic toxicities, at the investigator's discretion, the dose of pomalidomide may be increased to 4 mg beginning*

with cycle 4. Pomalidomide dose increases to 4 mg may also be considered in other situations on a case-by-case basis after discussion with the PI.

5.4.2.1 Mid-cycle pomalidomide dose reductions

Per modification rules in **Table 4** and **Table 5**, subjects may warrant pomalidomide dose reduction mid-cycle. Insurance and/or pharmacy delivery limitations may prevent receipt of a new bottle of pomalidomide at the reduced dose until the next cycle, and pomalidomide capsules cannot be cut in half. If this occurs, the treating clinician may do one of the following:

- A) Have the subject take one pill **EVERY OTHER DAY** of their current dose of pomalidomide, to complete the usual three weeks of pomalidomide for the current cycle and then switch to the new daily dose for next cycle
OR
- B) Remain off pomalidomide until the subject receives a new supply at the lower dose and is due to start the next cycle.

Decisions should be made at the discretion of the treating clinician based on the urgency of continuing pomalidomide and other relevant considerations such as subject's ability to comply with every other day dosing strategy.

As an example, a hypothetical subject is on 3 mg pomalidomide and on day 10 of the current cycle of Isa-Pom-Dex, the subject experiences a toxicity requiring pomalidomide dose reduction to 2 mg. The treating clinician has the following options: A) instruct the subject to take pomalidomide 3 mg every **OTHER** day until day 21 of the current cycle, followed by the standard 7-day break; or B) instruct the subject to remain off pomalidomide for the remainder of the current cycle. In either case, the subject would begin a pomalidomide dose of 2 mg on day 1 of the next cycle.

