5.4.2.2 Pomalidomide Dose Modifications for Specific Toxicities

Table 4 Pomalidomide Dose Modification for Hematologic Toxicity

Toxicity	Action / Considerations
Delay of >2 weeks due to cytopenias, per Criteria for Initiating a New Cycle of Treatment.	
 • If event is solely neutropenia, consider adding G-CSF and resuming at prior dose of pomalidomide. • For all other events, upon count recovery, reduce pomalidomide by one dose level.
Mid-cycle grade 4 thrombocytopenia (platelets < 25 × 10 ⁹ /L)	
 • Hold pomalidomide and continue other study therapies if clinically appropriate. • Consider holding VTE prophylaxis (aspirin or anticoagulation) if subject is currently taking it.

	
 Resume pomalidomide with one dose level reduction only when the subject's platelets recover to $\geq 50 \times 10^9/L$
Mid-cycle grade 4 neutropenia ($ANC < 0.5 \times 10^9/L$) OR any grade febrile neutropenia	
 Hold pomalidomide and continue other study therapies if event is not febrile neutropenia and continuing is felt to be clinically appropriate. Resume pomalidomide when ANC recovers to $\geq 1 \times 10^9/L$ and fever and/or infections, if present, have resolved. If investigator plans on adding G-CSF and no other indication for reducing study therapies exists, may resume pomalidomide at same dose. If subject was already on short-acting G-CSF ≥ 3 times weekly (e.g., Neupogen or Granix) or long-acting G-CSF at any frequency (e.g., Neulasta), OR investigator does not feel G-CSF is clinically appropriate, reduce pomalidomide one dose level. For each subsequent drop of ANC less than 0.5×10^9, pomalidomide will be held and other study therapies will continue if continuation is felt to be clinically appropriate. Pomalidomide will then resume with one dose-level reduction when ANC recovers to $\geq 0.5 \times 10^9/L$.

Table 5. Other Treatment Modifications/Delays for Non-Hematologic Toxicity

Adverse Event (Severity)	Action on Study Drugs	Further Considerations

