GI Grade ≥ 2 diarrhea	
 • Ensure supportive care (anti-motility agents, bile acid sequestrants, etc.) are maximized. • If diarrhea is attributed to pomalidomide, hold pomalidomide until resolution to Grade ≤ 1. • If event occurred without maximal supportive care (per discretion of the treating clinician), resume pomalidomide at prior dose with maximized supportive care. If event occurred despite maximal supportive care, reduce pomalidomide one dose level. 	
Peripheral Neuropathy:		
Consider workup for alternative causes such as amyloidosis, diabetic neuropathy, and also neurology evaluation, since study agents uncommonly cause neuropathy. Attributing progressive neuropathy to study therapy should be done very cautiously. Study treatment should not be held for worsening peripheral neuropathy that is not due to direct neurotoxicity of therapy, especially neuropathy that precedes study participation.		
Worsening grade 2 peripheral neuropathy with pain or new grade 2-3 peripheral neuropathy	
 • Hold pomalidomide until resolution to grade ≤ 1 or to prior baseline • Reduce pomalidomide to next lower dose upon recovery 	Grade 2 signs and symptoms: Moderate symptoms; limiting instrumental activities of daily living (ADL)
New or worsening grade 4 peripheral neuropathy	
 • Discontinue pomalidomide permanently 	
Skin Rash		
Grade 2-3 non-blistering rash	
 • If offending drug is felt to be pomalidomide, hold pomalidomide and reduce to next lower dose upon return to Grade ≤ 1 or baseline. 	Maximize supportive care such as H1 and H2 blockers and/or topical corticosteroid preparations. May use short-course (< 2 weeks) oral corticosteroids if felt to be warranted.
Grade 4 non-blistering rash	
 • Discontinue offending drug permanently. 	
Grade ≥ 3 blistering / desquamating skin rash or erythema multiforme	
 • Discontinue offending drug permanently. 	

Adverse Event (Severity)	Action on Study Drugs	Further Considerations

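### Section 5.4.2.1 gives no hold or recovery step before option A's every-other-day pomalidomide, while every mid-cycle reduction row in Tables 4 and 5 requires a hold until recovery.

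*Combined protocol and SAP*

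**What the plan says.** Section 5.4.2.1 ties itself to Tables 4 and 5: under their rules, "subjects may warrant pomalidomide dose reduction mid-cycle". It then describes a supply problem: "Insurance and/or pharmacy delivery limitations may prevent receipt of a new bottle of pomalidomide at the reduced dose until the next cycle". For that case it offers two options. Under option A the subject takes the current capsule every other day "to complete the usual three weeks of pomalidomide for the current cycle and then switch to the new daily dose for next cycle". Under option B the subject stays off pomalidomide until the lower strength has arrived and the next cycle is due. The choice is left to the treating clinician, who is to weigh how urgent it is to continue the drug and other considerations such as ability to comply. Recovery from the toxicity is not named.

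In the worked example a subject on 3 mg reaches day 10, when "the subject experiences a toxicity requiring pomalidomide dose reduction to 2 mg". Option A is then 3 mg every other "day until day 21 of the current cycle, followed by the standard 7-day break".

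Section 5.4.2.2 treats the same events differently. For mid-cycle grade 4 thrombocytopenia, Table 4 holds the drug and says "Resume pomalidomide with one dose level reduction only when the" platelet count is back to at least 50 × 10⁹/L. For neuropathy, Table 5 holds the drug until grade 1 or lower or prior baseline, and then says "Reduce pomalidomide to next lower dose upon recovery".

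**The concern.** The section that applies the tables leaves out the step with which the tables begin. The only condition that opens options A and B is that the lower-strength capsules are missing. A site that copies the day-10 example would keep dosing a subject at the current strength, on alternate days, from the toxicity to day 21. A site that works from Table 4 or 5 would stop the drug and wait for recovery. Section 11.5 requires conduct as the approved protocol describes, and each site could claim that it complied.

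Two things are at stake. One is subject safety: section 4.1.7 selects subjects for predicted high risk of severe toxicity, and the table rows include grade 4 cytopenias and febrile neutropenia. The other is uniform delivery of the regimen in a multicenter single-arm study, where the same event could lead to different pomalidomide exposure from site to site.

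**Working it through.** No design figure is involved. The check sets section 5.4.2.1 beside each row of Tables 4 and 5, then counts doses in the protocol's own example.

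**Step 1. Mid-cycle rows that can end in a pomalidomide reduction (section 5.4.2.2).**

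| Row | Hold first? | Threshold before resuming or reducing | Condition on the row |
|---|---|---|---|
| Table 4: grade 4 thrombocytopenia | Yes | Platelets ≥ 50 × 10⁹/L | None |
| Table 4: grade 4 neutropenia, or febrile neutropenia of any grade | Yes | ANC ≥ 1 × 10⁹/L and any fever or infection resolved; ANC ≥ 0.5 × 10⁹/L for each later drop | Same dose possible if G-CSF is added |
| Table 5: grade ≥ 2 diarrhea | Yes | Grade ≤ 1 | Attributed to pomalidomide; reduced only if it occurred despite maximal supportive care |
| Table 5: worsening grade 2 neuropathy with pain, or new grade 2–3 | Yes | Grade ≤ 1 or prior baseline | Introductory note: no hold for neuropathy not caused by therapy |
| Table 5: grade 2–3 non-blistering rash | Yes | Grade ≤ 1 or baseline | Pomalidomide felt to be the cause |
| Table 5: other grade 3 non-hematologic toxicity | Yes | Grade ≤ 1 or baseline | Judged related; listed exceptions |

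Result: 6 of 6 rows require a hold first. No row provides for a mid-cycle reduction without one.

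**Step 2. Rows left out, and why.** The delay of more than 2 weeks in Table 4 concerns the start of a cycle. Grade 4 neuropathy, grade 4 non-blistering rash, grade 3 or higher blistering rash and other grade 4 non-hematologic toxicity call for permanent discontinuation, not reduction.

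**Step 3. Section 5.4.2.1 against these rows.**
- Condition for using it: a reduction is due under the tables and the lower strength is not available.
- Hold stated in option A: no.
- Recovery threshold stated in option A: no.
- Hold or recovery stated in the day-10 example: no.
- Recovery named in the choice between A and B: no.

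**Step 4. Doses in the example.** If the first alternate-day dose falls on day s, the number of doses to day 21 is floor((21 − s)/2) + 1.
- s = 11 (days 11, 13, 15, 17, 19, 21): floor(10/2) + 1 = 6 doses; 6 × 3 mg = 18 mg.
- s = 12 (days 12, 14, 16, 18, 20): floor(9/2) + 1 = 5 doses; 5 × 3 mg = 15 mg.
- Hold with no recovery by day 21: 0 doses, 0 mg.

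The example gives no recovery date. The number of doses taken before recovery therefore runs from none, if the threshold is met before the first alternate-day dose, to all 5 or 6, if it is not met by day 21.

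**The case against.** The strongest reply is that the passages can be read together. Section 5.4.2.1 opens by invoking Tables 4 and 5 and nowhere says that it overrides them. In those tables a reduction takes effect after a hold, so the section may only answer which capsule to use once a recovered subject lacks the lower strength. Option B is worded as staying off the drug, which suggests that the drug has already been stopped.

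This reading is plausible, and part of it stands: the documents do not show an intent to dose through unresolved toxicity, and a reader who infers one goes too far. But the limit to recovered subjects is unstated. Option A and the example go from toxicity to alternate-day dosing with no step between, and the clinician is asked to weigh the urgency of continuing, not recovery.

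Other stronger readings are not supported:
- **The 1 mg level.** Section 5.4.2 says "If 1 mg is not tolerated despite maximal supportive care, then pomalidomide should be permanently discontinued", and a reader might infer that option A keeps such a subject on drug. But below 1 mg there is no reduced-dose bottle to await and no new daily dose to switch to, so option A does not apply.
- **Average dose.** Alternate-day 3 mg averages 3/2 = 1.5 mg/day against the 2 mg level in Table 3. Section 5.4.2.1 does not claim that they are equal; it presents alternate-day dosing as a workaround because capsules cannot be cut in half.
- **Frequency.** The 43% of Isa-Pom-Dex patients in ICARIA-MM with pomalidomide reductions (section 1.7.1) is not restricted to mid-cycle events or supply failure, and says nothing about the choice of option A.
- **Endpoints.** The toxicity boundary in section 10.2 counts grade 4 or higher non-hematologic events, for which Table 5 generally requires discontinuation. TFFS ends at discontinuation, and a hold alone is not that. No effect on either is shown.

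**Conclusion.** This is an internal inconsistency in a safety instruction, and it should be reconciled. Option A and its example carry no hold or recovery condition, whereas all the relevant table rows do. In the protocol's own example the literal difference is 15 or 18 mg of pomalidomide against none, if recovery has not come by day 21; earlier recovery narrows it.

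The conclusion rests on reading the example as written, with the first alternate-day dose on day 11 or 12. It also rests on the event being one for which the table row applies, including attribution to the drug where the row asks for it. The documents do not show how often the situation will arise, and the point does not depend on that. It takes no view on which instruction is clinically right.

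**What to change.** Reconcile section 5.4.2.1 with Tables 4 and 5:
- State in section 5.4.2.1 whether the hold and recovery thresholds of Tables 4 and 5 must be met before option A may be used.
- Rewrite the day-10 example so that it shows the same sequence as the rule.

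The clinical team decides which instruction governs. The cost is a few sentences in the next amendment and a memo to sites, with no added visits or tests.
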